10.1.4 Pregnancy reporting

Pregnancies

To ensure subject safety, each pregnancy occurring after signing the informed consent must be reported to Novartis within 24 hours of learning of its occurrence. The pregnancy should be followed up to determine outcome, including spontaneous or voluntary termination, details of the birth, and the presence or absence of any birth defects, congenital abnormalities, or maternal and/or newborn complications.

Pregnancy should be recorded and reported by the Investigator to the CMO&PS. Pregnancy follow up should be recorded on the same form and should include an assessment of the possible relationship to study treatment any pregnancy outcome. Any SAE experienced during pregnancy must be reported.

10.1.5 Reporting of study treatment errors including misuse/abuse

Medication errors are unintentional errors in the prescribing, dispensing, administration or monitoring of a medicine while under the control of a healthcare professional, subject or consumer (EMA definition).

Misuse refers to situations where the medicinal product is intentionally and inappropriately used not in accordance with the protocol.

Abuse corresponds to the persistent or sporadic, intentional excessive use of a medicinal product, which is accompanied by harmful physical or psychological effects.

Study treatment errors and uses outside of what is foreseen in the protocol will be recorded on the appropriate eCRF irrespective of whether or not associated with an AE/SAE and reported to Novartis Safety only if associated with an SAE. Misuse or abuse will be collected and reported in the safety database as SAEs within 24 hours of Investigator's awareness ([Table 10-1](#)).

[figure not shown]
Table 10-1 Guidance for capturing the study treatment errors including misuse/abuse

Treatment error type	Document in dosing eCRF (Yes/No)	Document in AE eCRF	Complete SAE form
Unintentional study treatment error	Yes	Only if associated with an AE	Only if associated with an SAE
Misuse/Abuse	Yes	Yes	Yes, even if not associated with a SAE

For more information on AE and SAE definition and reporting requirements, please see the, respective sections.

10.2 Additional safety monitoring

Not applicable.

11 Data collection and database management

11.1 Data collection

Designated Investigator staff will enter the data required by the protocol into the eCRF. The eCRFs have been built using fully validated secure web-enabled software that conforms to 21 CFR Part 11 requirements, Investigator site staff will not be given access to the EDC system until they have been trained. Automatic validation programs check for data discrepancies in the eCRFs, and allow modification and/or verification of the entered data by the Investigator staff.

The Investigator/designee is responsible for assuring that the data (recorded on eCRFs) (entered into eCRF) is complete, accurate, and that entry and updates are performed in a timely manner. The Investigator must certify that the data entered are complete and accurate.

After final database lock, the Investigator will receive copies of the subject data for archiving at the study site.

All data should be recorded, handled and stored in a way that allows its accurate reporting, interpretation and verification.

11.2 Database management and quality control

Novartis personnel (or designated contract research organization [CRO]) will review the data entered by investigational staff for completeness and accuracy. Electronic data queries stating the nature of the problem and requesting clarification will be created for discrepancies and missing values and sent to the study site via the EDC system. Designated Investigator site staff is required to respond promptly to queries and to make any necessary changes to the data.

[figure not shown]
Concomitant treatments and prior medications entered into the database will be coded using the WHO Drug Reference List, which employs the Anatomical Therapeutic Chemical classification system. Medical history/current medical conditions and AEs will be coded using the Medical dictionary for regulatory activities (MedDRA) terminology.

Laboratory samples will be processed centrally and the results will be sent electronically to Novartis (or a designated CRO).

Randomization codes and data about all study treatments dispensed to the subject and all dosage changes will be tracked using an NIRT system. The randomization list will be generated by a vendor who will transfer it after the RRS has been approved. Later this will be uploaded into the NIRT system.

Each occurrence of a code break via NIRT will be reported to the clinical team and monitor. The code break functionality will remain available until study shut down or upon request of Novartis.

Once all the necessary actions have been completed and the database has been declared to be complete and accurate, it will be locked. Any changes to the database after that time can only be made after written agreement by Novartis development management.

11.3 Site monitoring

Before study initiation, at a site initiation visit or at an Investigator's meeting, a Novartis/delegated CRO representative will review the protocol and data capture requirements (i.e., eCRFs) with the Investigators and their staff. During the study, Novartis employs several methods of ensuring protocol and GCP compliance and the quality/integrity of the sites' data. The field monitor will visit the site to check the completeness of subject records, the accuracy of data capture/data entry, the adherence to the protocol and to GCP, the progress of enrollment, and to ensure that study treatment is being stored, dispensed, and accounted for according to specifications. Key study personnel must be available to assist the field monitor during these visits. Continuous remote monitoring of each site's data may be performed by a centralized Novartis/delegated CRO. Additionally, a central analytics organization may analyze data & identify risks & trends for site operational parameters, and provide reports to Novartis clinical teams to assist with study oversight.

The Investigator must maintain source documents for each subject in the study, consisting of case and visit notes (hospital or clinic medical records) containing demographic and medical information, laboratory data, ECGs, and the results of any other tests or assessments. All information on eCRFs must be traceable to these source documents in the subject's file. The Investigator must also keep the original informed consent form signed by the subject (a signed copy is given to the subject).

The Investigator must give the monitor access to all relevant source documents to confirm their consistency with the data capture and/or data entry. Novartis monitoring standards require full verification for the presence of informed consent, adherence to the inclusion/exclusion criteria, documentation of SAEs, and of data that will be used for the primary endpoint. Additional checks of the consistency of the source data with the eCRFs are performed according to the study-specific monitoring plan. No information in source documents about the identity of the subjects will be disclosed.

[figure not shown]
12 Data analysis and statistical methods

All analyses will be performed by Novartis or a designated CRO. Any data analysis carried out independently by the Investigator should be submitted to Novartis before publication or presentation.

Continuous variables will be summarized by number of subjects, mean, standard deviation, minimum, median, and maximum. For selected parameters, 25th and 75th percentiles will also be presented. Categorical variables will be summarized by frequencies and percentages.

In addition to the statistical methods outlined below, further details and any additional exploratory analyses that may be performed will be described in the Statistical Analysis Plan.

The last available assessment on or before the start date of study treatment (i.e., secukinumab or guselkumab) is taken as the baseline assessment.

12.1 Analysis sets

The following analysis sets will be used in this study:

The FAS comprises all subjects to whom study treatment has been assigned by randomization. According to the intent-to-treat principle, subjects will be analyzed according to the treatment they have been assigned to during the randomization procedure.

The Safety Set includes all subjects who receive at least one dose of study treatment. Subjects will be analyzed according to the study treatment received.

12.2 Subject demographics and other baseline characteristics

12.2.1 Demographics and baseline characteristics

Demographic and other baseline data including disease characteristics will be listed and summarized descriptively by treatment arm for the FAS.

12.2.2 Medical history

Relevant medical histories and current medical conditions at Screening will be listed and summarized by system organ class and preferred term for each treatment arm for the FAS.

12.3 Treatments

The Safety Set will be used for the analyses below.

12.3.1 Study treatments

The duration of exposure to secukinumab and guselkumab (in weeks), will be summarized by means of descriptive statistics. In addition, the number and percentage of subjects with cumulative exposure levels (e.g., any exposure, ≤ 1 week, ≤ 2 weeks, ≤ 3 weeks, ≤ 4 weeks, ≤ 8 weeks, etc.) will be presented.

The number of subjects with dose adjustments (reductions, interruption, or permanent discontinuation) and the reasons thereof will be summarized. All dosing data will be listed.

12.3.2 Prior and concomitant treatments

Concomitant medications and significant non-drug therapies prior to and after the start of the study treatment will be listed and summarized according to the Anatomical Therapeutic Chemical (ATC) classification system by treatment arm.

12.4 Analysis of the primary endpoint

12.4.1 Definition of primary endpoint

The primary objective is to assess the superiority of secukinumab over guselkumab in controlling clinical activity in psoriatic plaques resistant to treatment with ustekinumab.

The primary endpoint is the proportion of subjects whose plaque achieves “clear” or “almost clear” status (TCS = 0-2) by 16 weeks of treatment with secukinumab or guselkumab.

12.4.2 Statistical model, hypothesis, and method of analysis

The number (%) of subjects whose plaques achieve “clear” or “almost clear” status (TCS = 0-2) at Week 16 (i.e., responders) will be provided based on the FAS together with the 95% confidence interval using the exact method for the difference in proportions of responders in each arm.

Furthermore, a 1-sided Fisher’s exact test for the difference in the proportions of responders in the secukinumab (P1) and gesulkumab (P2) arms, $H_0: P_1 - P_2 = 0$ versus $H_1: P_1 - P_2 > 0$ at a Type I error rate of 0.05 will be performed.

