6.1.3 Treatment arms

At Baseline, subjects will be randomized to one of the 2 treatment arms in a 1:1 ratio ([Figure 3-1](#)).

Secukinumab treatment arm: 20 subjects with plaque psoriasis with an inadequate response to ustekinumab will self-administer 300 mg secukinumab as two 150-mg s.c. injections at Baseline, Weeks 1, 2, 3, 4 and then every 4 weeks until Week 12 inclusive.

Guselkumab treatment arm: 20 subjects with plaque psoriasis with an inadequate response to ustekinumab will self-administer guselkumab as 100-mg s.c. injections at Baseline, Weeks 4, and 12.

[figure not shown]
The initiation of secukinumab and guselkumab should not happen earlier than 12 weeks from the last administration of ustekinumab.

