12.9 Sample size calculation

12.9.1 Primary endpoint

A total of 40 subjects will be enrolled in this study i.e., 20 subjects per treatment arm. Based on the feedback from dermatologists with experience in prescribing biologic treatments for psoriasis (there is no historical data in the literature), the response rates to treatment are assumed to be 35% for guselkumab and 75% for secukinumab.

Table 12-1 presents the 95% exact confidence interval for different P1 (proportion of responders in the secukinumab arm) and P2 (proportion of responders in the guselkumab arm) and their corresponding difference P1-P2, together with the estimated power of a 1-sided Fisher's exact test at the target 1-sided Type I error rate of 5%.

For the favorable P1 = 0.75 and P2 = 0.35 values, the Fisher's exact test at the target Type I error of 5% will correctly reject H0: P1-P2 ≤ 0 with the power of 0.72%.

Table 12-1 Exact 95% confidence intervals for P1 and P2, the corresponding difference P1-P2, and the estimated power of the Fisher's exact test for different P1 and P2 values

Proportion (number) of responders in the secukinumab arm at Week 16: P1	Proportion (number) of responders in the guselkumab arm at Week 16: P2	95% exact confidence interval for P1	95% exact confidence interval for P2	95% exact confidence interval for P1-P2	Power of a 1-sided Fisher's exact test: H1: P1-P2 > 0
0.60 (12)	0.20 (4)	(0.36, 0.80)	(0.05, 0.43)	(0.10, 0.66)	75%
0.65 (13)	0.25 (5)	(0.40, 0.84)	(0.08, 0.49)	(0.06, 0.66)	72%
0.70 (14)	0.30 (6)	(0.45, 0.88)	(0.11, 0.54)	(0.09, 0.64)	71%
0.75 (15)	0.30 (6)	(0.50, 0.91)	(0.11, 0.54)	(0.13, 0.70)	82%
0.75 (15)	0.35 (7)	(0.50, 0.91)	(0.15, 0.59)	(0.06, 0.66)	72%
0.75 (15)	0.40 (8)	(0.50, 0.91)	(0.19, 0.63)	(0.01, 0.62)	61%
0.80 (16)	0.40 (8)	(0.56, 0.94)	(0.19, 0.63)	(0.10, 0.66)	75%

13 Ethical considerations and administrative procedures

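### The primary test (1-sided 5% Fisher) and the reported interval (two-sided 95% exact) use different levels and procedures, so they can disagree at the margin, and Fisher spends only 2.7% of the 5% allowed

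*Protocol*

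**What the plan says.** Protocol section 12.4.2 gives two outputs for the primary endpoint in the full analysis set. The first is the number and percentage of responders, "together with the 95% confidence interval using the exact method for the difference in proportions of responders in each arm". The second is a 1-sided Fisher's exact test of secukinumab (P1) against guselkumab (P2) "at a Type I error rate of 0.05 will be performed". The Data analysis row of the protocol summary has the same structure.

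Section 12.9.1 repeats the level ("exact test at the target 1-sided Type I error rate of 5" percent) and gives the size: "A total of 40 subjects will be enrolled in this study i.e., 20 subjects per treatment arm". Section 6.1.3 gives equal allocation. For planning, "the response rates to treatment are assumed to be 35% for guselkumab and 75% for secukinumab". Table 12-1 has a column headed "95% exact confidence interval for P1-P2" with two limits per row, beside the power of the Fisher test.

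The interval method is named only as exact. The protocol does not link the interval to the test or say how to read a result on which they differ.

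**The concern.** A 1-sided 5% test agrees with a one-sided 95% lower limit, which is the lower end of a two-sided 90% interval. The planned interval is two-sided 95%, so its lower end works at 2.5%. The procedures differ too. Fisher's test conditions on the total number of responders and does not invert to an interval for a difference in proportions. An exact interval for that difference has to come from another construction, normally an unconditional one.

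The report could therefore declare superiority beside an interval for the treatment difference that includes 0. In a 40-subject trial whose only formal objective is superiority, that would be awkward to defend. The comparison also shows that the chosen test uses little more than half of the error rate it is allowed.

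**Working it through.** **Inputs.** n = 20 per arm (12.9.1, 6.1.3); 1-sided level 0.05 (12.4.2, 12.9.1); two-sided 95% interval, hence 0.025 per side (12.4.2, Table 12-1); planning rates 0.75 and 0.35 (12.9.1). The ordering behind the exact interval is not stated, so score ordering is an assumption.

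**1. Reproduce the stated power.** For x secukinumab and y guselkumab responders, t = x + y:

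Fisher p(x, y) = Σ over k ≥ x of C(20,k)·C(20,t−k) / C(40,t)

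Power = Σ over outcomes with p ≤ 0.05 of Bin(x; 20, P1)·Bin(y; 20, P2)

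Over all 21 × 21 = 441 outcomes, 119 are significant. The power for the seven Table 12-1 rows rounds to 75, 72, 71, 82, 72, 61 and 75%, as printed. At 0.75 v 0.35 it is 72.4%. (The running text of 12.9.1 says "with the power of 0.72" followed by a percent sign, which is a misprint for 72%.)

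**2. A conflicting outcome.** For 10 v 4, t = 14:

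- Numerator: 184,756·4,845 + 167,960·1,140 + 125,970·190 + 77,520·20 + 38,760·1 = 1,112,140,680
- Denominator: C(40,14) = 23,206,929,840
- p = 0.0479, so superiority is declared. By symmetry 16 v 10 gives the same p.

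The interval includes 0 when the exact unconditional 1-sided p at zero difference, maximised over the common response rate, exceeds 0.025. The score statistic is z = (x−y)/20 ÷ √(2·p̄(1−p̄)/20). For 10 v 4, p̄ = 14/40 = 0.35 and z = 0.30/√(0.2275·0.1) = 1.99. The results for both outcomes are:

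| Construction | p at zero difference | 95% interval includes 0? |
|---|---|---|
| Score ordering, 1-sided | 0.0267 (> 0.025) | yes |
| Raw-difference ordering, 1-sided | 0.0403 (> 0.025) | yes |
| Score, single 2-sided test | 0.0534 (> 0.05) | yes, about −0.005 to 0.565 |

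With score ordering these two are the only conflicts of this kind among the 119 significant outcomes.

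**3. Probability of conflict, score ordering.** Bin(10; P1)·Bin(4; P2) + Bin(16; P1)·Bin(10; P2).

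- 0.75 v 0.35: 0.0099·0.0738 + 0.1897·0.0686 = 0.0007 + 0.0130 = 1.4%
- 0.75 v 0.40: 2.3%
- All seven Table 12-1 scenarios: about 0.7% to 2.6%

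At the seven outcomes tabulated there is no conflict: Fisher p runs from 0.005 to 0.027 and every printed lower limit is above 0.

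**4. Error rate and power of the alternatives.** Maximum size is the largest rejection probability over a common response rate.

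| Test, 1-sided 0.05 | Rejecting outcomes | Maximum size | Power at 0.75 v 0.35 |
|---|---|---|---|
| Fisher | 119 | 2.7% | 72.4% |
| Score-ordered exact unconditional | 119 + 11 = 130 | 4.3% | 80.9% |

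The score-ordered test rejects wherever Fisher does. The 11 added outcomes are 3 v 0, 4 v 0, 7 v 2, 11 v 5, 12 v 6, 13 v 7, 14 v 8, 15 v 9, 18 v 13, 20 v 16 and 20 v 17. The gain is 80.9 − 72.4 = 8.5 points.

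**5. Smaller changes.**

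- Fisher at 0.05 with a score-ordered 90% interval: outcomes that are significant with 0 inside the interval fall from 2 to 0. The 11 outcomes above then have an interval excluding 0 and Fisher p > 0.05.
- The 95% interval kept and Fisher run at 0.025: the same conflicts fall to 0 with score ordering, but power at 0.75 v 0.35 drops from 72.4% to 61.4%.

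**The case against.** Four objections have weight.

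*The decision rule is not in doubt.* A reader might infer that the plan leaves open whether the test or the interval carries the claim. It does not. In 12.4.2 the hypotheses and the error rate attach only to the Fisher test, and 12.9.1 powers the study on that test alone. The interval accompanies the percentages. This stands in full.

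*The error rate is sound.* A reader might take the mismatch as a sign of inflated Type I error. Fisher's maximum size of 2.7% rules that out. A 1-sided test beside a conventional 95% interval is also common reporting practice in Phase 2a.

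*The conflict is rare.* An interval ordered on the raw difference would give 14 conflicting outcomes, and probabilities of 9.5% at 0.80 v 0.50 and 14% at 0.85 v 0.55. The protocol does not support those figures. Raw-difference ordering gives one interval, about 0.07 to 0.67, for all five Table 12-1 rows with a difference of 0.40, yet the table prints three: (0.10, 0.66), (0.06, 0.66) and (0.09, 0.64). Those two pairs of rates are not planning scenarios either. No single exact method tried reproduces the whole column, so the table does not establish score ordering; it only counts against the raw-difference figures.

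*Detail may sit in the SAP.* Section 12 defers further details there, and the name of the interval method may be among them. That the interval comes from a different procedure is an inference, though a safe one given how Fisher's test is built. The 95% level, the 1-sided 5% level and the choice of Fisher are fixed in the protocol itself, so the point does not depend on what the SAP adds.

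**Conclusion.** The point holds as a mismatch between test and interval and as a loss of efficiency. It is not an error-rate defect or an undefined decision rule. Two outcomes, 10 v 4 and 16 v 10, are declared superior with a 95% exact interval that includes 0. Under score ordering the chance of this is 1.4% at the planning rates and at most about 2.6% across the Table 12-1 scenarios.

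The larger practical matter is that Fisher uses 2.7% of an allowed 5%. A score-ordered exact unconditional test stays within 5% (maximum 4.3%), has about 8.5 points more power at 0.75 v 0.35, and supplies an interval that agrees with it.

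These figures assume exactly 20 analysed subjects per arm, independent binomial responses and, for the conflict probabilities, a score-ordered interval. The planning rates rest on clinicians' feedback without historical data, so the probabilities are indicative.

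**What to change.** Preferred change:

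- In 12.4.2 and the protocol summary, replace Fisher's test with one named exact unconditional procedure at 1-sided 0.05. The score-ordered version is the simplest, because it inverts directly to an interval for the difference. Boschloo's test is an alternative for the decision, but its extension to non-zero differences must then be defined to obtain the interval.
- Report the two-sided 90% interval (one-sided 95% lower limit) from inverting that same test as the interval that matches the decision. Keep the 95% interval and label it descriptive.
- Recompute the power and difference-interval columns of Table 12-1 with the named method, and restate the power sentence in 12.9.1, correcting its misprint.

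This needs no more subjects, visits or data. It does change the primary analysis, so it requires a protocol amendment and matching SAP text before data are seen. The 90% interval looks less strict than a 95% interval and must be clearly labelled.

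If the sponsor keeps Fisher, add a score-ordered 90% interval, state that Fisher governs, and label the 95% interval descriptive. That removes the outcomes that are significant with 0 inside the interval (2 to 0). It leaves 11 outcomes where the 90% interval excludes 0 and Fisher is not significant, and it forgoes the gain in power.

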6.3.2 Treatment assignment, randomization

At the Baseline Visit, all eligible subjects will be randomized to one of the treatment arms via the Novartis Interactive Response Technology (NIRT). After confirming that the subject fulfills all the inclusion/exclusion criteria, the Investigator or delegate will contact the NIRT and randomize the subject. The NIRT will assign a randomization number to the subject and allocate the subject to a treatment arm. The treatment allocation will be confirmed in the NIRT and communicated to the Investigator or designee, who will dispense the medication accordingly.

The randomization numbers will be generated using the following procedure to ensure that treatment assignment is unbiased from subjects and Investigator staff. A subject randomization list will be produced by the NIRT provider using a validated system that automates the random assignment of subject numbers to randomization numbers. These randomization numbers are linked to the different treatment arms.

The randomization scheme for subjects will be reviewed and approved by a member of the Randomization Office.

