Subjects should be seen for all visits/assessments as outlined in the assessment schedule or as close to the designated day/time as possible. Missed or rescheduled visits should not lead to automatic discontinuation. Subjects who prematurely discontinue the study for any reason should be scheduled for a visit as soon as possible, at which time all of the assessments listed for the final visit will be performed. At this final visit, all dispensed investigational product should be reconciled, and the AEs and concomitant medications recorded on the eCRF.

[REDACTED]

Table 8-1 Assessment schedule

Visit name	Screening	Baseline	End of study	Unscheduled
Visit number	1	2	3	-
Week	-4 to -1	-	16	-
Day	-28 to -1	1	112	-
Informed consent	X			
Inclusion/exclusion criteria	X	X		
Pregnancy test ²	X	X		
Randomization via NIRT		X		
Physical examination	X	X	X	X
Smoking history	X			
Medical history	X			
Relevant family history	X			
Demography	X			
Psoriasis medical and treatment history	X			
QFT	X			
Skin type	X			
Body temperature (°C)	X	X		
Height (cm)	X			
Weight (Kg)	X	X	X	
Vital signs	X	X	X	
Electrocardiogram	X			
Laboratory assessments	X		X	
Adverse events ³	X	X	X	X
Drug administration record		X	X	X
Concomitant medications	X	X	X	X
TCS of target plaque	X	X	X	X
Skin biopsies ██████████ ⁶		X	X	
Information on study completion			X	

Baseline Visit (Visit 2) should be conducted within 28 days of the Screening Visit (Visit 1).

Unscheduled visits can be decided by the Investigators according to their own clinical judgment and practice.

End-of-study assessments (Visit 3) should be conducted only on subjects who complete 4 to 16 weeks of treatment. There will be a \pm 2-day window for Visit 3 (Week 16)

- [REDACTED]
- 2) Performed on serum for women of childbearing potential
 - 3) SAEs collected up to 30 days after the last administration of study treatment

[REDACTED]

6) At Baseline, two 6-mm punch biopsies will be taken, one from the identified active plaque (TCS \geq 6) and one from never-lesional skin. At the End-of-study Visit, one biopsy will be taken from the same area of the plaque sampled at Baseline. Biopsies should be sampled from the trunk whenever possible to avoid scars in exposed areas of the body

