12.4.4 Sensitivity and supportive analyses

Analysis of the primary endpoint as observed i.e., without missing data imputation (as described in [Section 12.4.3](#)) will be performed as a sensitivity analysis for the primary endpoint.

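### The primary Fisher's exact test is valid but leaves Baseline TCS unused; one pre-specified cut into two strata would add robustness, and some power if Baseline TCS is prognostic

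*Protocol*

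**What the plan says.** Protocol 12.4.1 and 12.4.2 define a responder by an absolute TCS of 0-2, whatever the starting score. The arms are compared on the FAS by a 1-sided "exact test for the difference in the proportions of responders in the secukinumab (P1) and gesulkumab (P2) arms" at the 5% level, beside an exact 95% interval for the crude difference.

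Inclusion criterion 4 (5.1) asks for a TCS of at least 6, and 8.3.1 ends the scale at 9. Table 8-1 schedules "TCS of target plaque" at Screening, Baseline and End of study, and 8.3.1 places the Baseline score before the first dose.

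On allocation, 6.1.3 says that "subjects will be randomized to one of the 2 treatment arms in a 1:1 ratio", and 6.3.2 that "A subject randomization list will be produced by the NIRT provider using a validated system". Neither section names a stratification factor. The only supplementary analysis in 12.4.4 is "Analysis of the primary endpoint as observed i.e., without missing data imputation".

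On size, 12.9.1 states "A total of 40 subjects will be enrolled in this study i.e., 20 subjects per treatment arm" and "the response rates to treatment are assumed to be 35% for guselkumab and 75% for secukinumab", giving 72% power in Table 12-1.

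**The concern.** A plaque entering at TCS 6 has to fall 4 points to count as a response; one entering at 9 has to fall 7. Baseline TCS is therefore a natural candidate predictor of response, measured on the outcome's own scale at no extra cost. With 40 subjects and no stratification described, the arms can differ in Baseline severity by chance. If Baseline TCS does predict response, that difference carries into the responder comparison, and nothing in the planned test takes it out. The stakes are some unused power in a trial planned at 72%, and an avoidable question about Baseline balance when the result is read.

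**Working it through.** **Inputs.** From the Protocol: 20 per arm, response rates 0.75 and 0.35, 1-sided 5% level (12.9.1); Baseline TCS 6 to 9 (5.1, 8.3.1); no strata (6.1.3, 6.3.2). Not given, hence assumed: the Baseline TCS distribution and its relation to response.

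**1. The plan's own figure.** Power = Σ Bin(a; 20, 0.75) · Bin(b; 20, 0.35) over all (a, b) with P(X ≥ a) ≤ 0.05, where X is hypergeometric: 20 drawn from 40, of which a + b are responders. The result is 72.4%, against 72% in Table 12-1. The seven rows give 75.4, 72.4, 71.3, 82.3, 72.4, 61.0 and 75.4%, against 75, 72, 71, 82, 72, 61 and 75% stated. The table reproduces.

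**2. Fall needed.** 6 − 2 = 4 points at the lowest eligible score; 9 − 2 = 7 at the highest.

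**3. Chance imbalance.** Suppose 20 of the 40 plaques are high-TCS. The number k in one arm has P(k) = C(20, k) · C(20, 20 − k) / C(40, 20), and the arms differ by |2k − 20| subjects.

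| Difference between arms | Values of k | Probability |
|---|---|---|
| at least 4 subjects (20 points) | ≤ 8 or ≥ 12 | 34% |
| at least 6 subjects (30 points) | ≤ 7 or ≥ 13 | 11% |
| at least 8 subjects (40 points) | ≤ 6 or ≥ 14 | 2.6% |

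**4. The stratified test.** Let T be the secukinumab responders summed over strata. Given the margins in each stratum, the null distribution of T is the convolution of the stratum hypergeometrics. Reject if P(T ≥ t) ≤ 0.05.

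**5. Power with two strata, latent-correlation model.** Assumed Baseline weights for 6, 6.5, …, 9 are .30, .20, .20, .10, .10, .05, .05, so a cut at 6.5 puts .30 + .20 = 50% in the low stratum. There were 20,000 trials per row (simulation standard error √(0.72 × 0.28 / 20,000) ≈ 0.3 points).

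| Latent correlation | Fisher | Two strata | Gain (points) |
|---|---|---|---|
| 0 | 72.5% | 73.1% | 0.6 |
| 0.2 | 73.0% | 74.4% | 1.4 |
| 0.35 | 72.4% | 75.5% | 3.1 |
| 0.5 | 72.4% | 78.0% | 5.6 |

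With a skewed Baseline (only 5 to 15% of plaques above the cut) there is still no loss. The gain is about 1 point at 0.2 and about 1 to 3 points at 0.35.

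**6. A second model, and more strata.** Here the link is an odds ratio of response between the lowest and highest stratum, with the marginal rates held at 0.75 and 0.35. The unstratified test has about 72.4% throughout.

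| Strata | OR 1 | OR 2 | OR 4 | OR 10 |
|---|---|---|---|---|
| 2 (50/50) | 72.7% | 73.9% | 77.5% | 82.8% |
| 2 (70/30) | 72.3% | 73.8% | 76.8% | 81.0% |
| 4 | 70.7% | 71.1% | 73.7% | 75.7% |
| 7 (every half point) | 65.9% | 66.8% | 67.7% | 70.7% |

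Two strata do not lose power beyond simulation error. Four lose about 1 to 2 points when Baseline TCS is weakly prognostic or not prognostic; seven lose about 2 to 6 points throughout.

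**7. Type I error.** Averaged over randomization, Fisher's test has size of about 2.0 to 2.6%, and the stratified test 2.1 to 2.7%. Both are below 5%. Conditional on low-TCS subjects splitting 13 v 7 in favour of secukinumab, the size of Fisher's test is 4.6% at null response rates of 0.6 (low TCS) and 0.4 (high TCS), 6.4% at 0.7 and 0.4, and 10.6% at 0.8 and 0.3.

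**The case against.** The strongest reply is that nothing here is wrong. Fisher's test matches the stated hypothesis, the crude difference and the sample size, and randomization already accounts for chance imbalance. That stands. A reader might infer from the conditional sizes of 6.4% and 10.6% that the primary test inflates the Type I error. It does not. Those figures need a split of 13 v 7 in one direction together with strong assumed prognosis; a split at least that uneven in that direction has probability of about 11% / 2 ≈ 6% when half the plaques are high-TCS. Averaged over allocations, the size is well under 5%.

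A reader might also infer that stratifying costs nothing in general. That fails too: four or seven strata can lose power, and a common-odds-ratio test no longer corresponds to the planned exact interval for P1 − P2.

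Third, the prognostic value of Baseline TCS is unproven. The Protocol gives no data on it, 12.9.1 says that no historical response data exist, and the eligible range covers only the top third of the scale. This limits the likely gain, but does not remove the case for a change that loses no power at zero correlation.

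Last, adjusted supportive analyses are often left to the SAP. That is fair for the supportive role. But the Protocol itself fixes the primary test, and Section 12 leaves the SAP further details and exploratory analyses, so the choice of primary test can be assessed here.

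**Conclusion.** The point holds as an optional improvement. The primary test is valid, but ignores a Baseline measurement that sets the distance to the response threshold and that the described randomization does not balance. With exactly two strata, power is about 73% against 72% if Baseline TCS is not prognostic, and rises by about 1 to 6 points at latent correlations of 0.2 to 0.5; size stays below 5%. The gain rests on an assumed Baseline distribution and assumed correlations; the 34% and 11% imbalance figures rest on an even split of plaques. The documents do not show that Baseline TCS predicts response, and nothing here is a fault in Type I error control.

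**What to change.** Pre-specify a 1-sided exact conditional test of treatment with two Baseline TCS strata and one cut, for example 6.5 or less against above 6.5, at the 5% level. Report the stratified estimate beside the crude difference. Fix the cut before any data are seen: 6.4 leaves the trial team open to treatment, so a later choice would carry little weight. The 6.5 value is only an example, since the Protocol offers no basis for a particular cut. Do not stratify more finely.

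There are two ways to place it:

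- **As primary, in 12.4.2.** Align the confidence interval with the stratified test and restate the Table 12-1 power with the assumed Baseline split and prognostic strength.
- **As supportive, in 12.4.4.** Keep Fisher's test, its interval and Table 12-1 as they are, and name the stratified test as a pre-specified supportive analysis.

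No new data are needed, because inclusion criterion 4 already requires a Baseline TCS. The cost is Protocol and SAP wording, a few lines of code and one more estimate to report, plus the changes to the interval and power table if the test becomes primary.
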